**The Effect of Leukocyte Platelet
Rich Fibrin (L-PRF) Membrane in
The treatment of Localized
Gingival Recession
(Randomized Controlled Clinical
Study)**

Methodology

Date:3/11/2020

Sample selection and assignment:

Twenty patients who were diagnosed with Miller class I and II gingival recession, participated in this prospective clinical trial.

The patients were recruited from the outpatient clinic of Oral Medicine, Periodontology, oral Diagnosis and Radiology Department, Faculty of Dentistry, Ain Shams University. The purpose of the study was explained to all patients and an informed consent was signed before the conduction of the study. The proposal was presented to the faculty of Dentistry Ain Shams University Research Ethics committee and was approved before starting the research with number (453).

Patient selection:

Inclusion Criteria:

- 1- Systemically healthy patients (*American Society of Anesthesiologists I; ASA I*).
- 2- Age range (20 -40) years.
- 3- Good compliance with the plaque control instructions following initial therapy.

Patients: Materials and Methods

- 4- Patients diagnosed with localized gingival recession ***Miller*** class I or II in anterior and premolar teeth (maxillary or mandibular)
- 5- Availability for follow up and maintenance program.

Exclusion criteria:

1. Patient suffering from periodontitis
2. Presence of smoking habit.
3. Presence of occlusal interferences.
4. Pregnant and lactating females.
5. Vulnerable group of patients (handicapped, mentally retarded and prisoners) (according to the recommendation of esthetical committee of Faculty of Dentistry Ain Shams University).
6. Carious teeth and teeth with periapical infection.

Calculation of Power analysis:

The study consisted of two groups; **group (I) and group (II)** each group included 10 patients. The number of patients in each group was determined by sample size calculation based upon the results of *Tunali et al. (2015)*. Using alpha level of 0.05 (5%) and β level of 0.20 (20%) i.e. power = 80%; the estimated minimum required sample size was approximately 4 cases in each group. Patients were randomly selected using computer generated randomization (www.randomizer.org). Allocation concealment was achieved using a sealed coded opaque envelope containing treatment of the subject.

Grouping Criteria:

Group I: (L-PRF+ coronally repositioned flap):

Included 10 patients who received L-PRF membrane with coronally repositioned flap for the treatment of gingival recession

Group II: (Sub epithelial connective tissue+ coronally repositioned flap):

Included 10 patients who received sub-epithelial connective tissue graft with coronally repositioned flap for the treatment of gingival recession

III- Clinical parameters Assessments:

For the selected sites, the following clinical parameters were assessed using periodontal probe (UNC-15) * preoperative (baseline), 3, 6 and 9 months after the surgical procedure.

1. Plaque index (*Silness and Löe 1964*).
2. Gingival Index (*Löe and Silness 1963*).
3. Probing depth (PD) (*Glavind and Loe, 1967*).
4. Clinical attachment level (CAL) (*Glavind and Loe 1967*).
5. Gingival recession depth.
6. Keratinized tissue width.

* UNC15 Single-ended, color-coded probe. ergonomic handle. University of North Carolina, Hu Friedy, USA.

Patients: Materials and Methods

- **Pre surgical therapy:**

- Full Conventional periodontal treatment including supra, sub-gingival scaling and root planning were performed using ultra sonic[†] and hand scalers[‡] and hand curettes[§].
- Oral hygiene instructions (regular brushing 2 times/day and flossing) were repeated until patients had achieved a proper level of oral hygiene where plaque index (PI) and gingival index (GI) ≤ 1 .

[†] Woodpecker UDS-K LED Ultrasonic Scaler EMS Compatible, Faye dental professional supplies, China

[‡] Sickle scaler, posterior jacquette, Hu-Friedy ,USA

[§] Universal Curettes(2R/2L),(4R/4L), Hu-Friedy ,USA

IV-Surgical protocol:

Group (I)

- 1) Anesthesia (Articaine HCL 4% containing epinephrine at a concentration of 1:100,000)** was administrated at the recession area.
- 2) An intrasulcular incision was made with a surgical blade (15c)^{††} on the buccal aspect of the involved tooth. The incision was extended horizontally to dissect the facial aspect of the adjacent papillae both mesially and distally.
- 3) Two oblique releasing incisions were made mesial and distal to the horizontal incision beyond the mucogingival junction.
- 4) A full-thickness flap was raised with a periosteal elevator up to the mucogingival junction. A partial-thickness dissection was done apically, leaving the underlying periosteum in place.
- 5) A mesio-distal and apical dissection parallel to the vestibular lining mucosa was performed to release residual muscle tension and facilitate the passive

** Artinibsa 40mg/0.01mg/ml solution for Sc/IM injection, epinephrine 1:100000,cartridges of 1.8ml ,inibisa dental, Spain

†† Trinon15c sterile scalpel Blades ,Germany

Patients: Materials and Methods

coronal displacement of the flap. The papillae adjacent to the involved tooth were de epithelialized.

- 6) After flap reflection debridement^{‡‡} was done to the root surface for removal of necrotic cementum from the root surface.
- 7) Just prior to surgery a 10 ml intravenous blood was obtained from the median antecubital vein of the patient, put in glass test tube^{§§} without additives and centrifuged*** immediately at 2700 revolutions per minute for 12 minutes at room temperature for L-PRF preparation.
- 8) Coagulation started immediately and three parts quickly appear in the tube: a packed red blood cell at the bottom, acellular plasma at top and the L -PRF clot in between.
- 9) The L-PRF clot was extracted from the tube and it was cut from the blood clot using a surgical blade (15c)^{†††} , the clot was then placed in the PRF box to obtain a membrane.

^{‡‡} Universal Curettes(2R/2L),(4R/4L), Hu-Friedy ,US

^{§§} Dry Vacutube, Biocon®, Brazil

^{***} PRF CENTRIFUGE (Duo machine), UNSPSC code 41100000 (Ostralos Ltd, New Zealand)

^{†††} Trinon sterile scalpel Blades ,Germany

Patients: Materials and Methods

10) The L-PRF membrane was fixed at the site then the flap was coronally repositioned by sling suturing technique using 5-0 polypropylene sutures^{†††}.

Fig (1): PRF centrifugation machine

^{†††} Assut Sutures, non Absorbable (Polypropylene) 5-0 USP, braided violet coated 3/8 rev.cutt.17mm, AM trading, Switchezland

Group (II)

As group I from step number 1 to step number 6

- 7) Infiltration anesthesia was given in the palate anteriorly and posteriorly to the area of sub epithelial connective tissue graft harvesting.
- 8) Sub epithelial connective tissue graft was obtained from the palate using surgical blade 15c §§§ through a single incision technique approximately 3 mm apical to the gingival margin of the maxillary teeth. An incision was made perpendicular to the palatal tissue until reaching the bone in a horizontal direction. Partial thickness incision was done to separate the sub epithelial connective tissue from the covering palatal epithelium, then using a small mucoperiosteal elevator the tissue was dissected from the palatal bone and the graft was cut from both sides. The palatal tissues were sutured with x suture using 5-0 polypropylene **** sutures.
- 9) The sub epithelial connective tissue was fixed at the recipient site using resorbable 5-0 vicryl

§§§Trinon sterile scalpel Blades ,lot0483,Germany

**** Assut Sutures, non Absorbable (polypropylene) 5-0 USP, braided violet coated 3/8 rev.cutt.17mm, AM trading, Switchezland

Patients: Materials and Methods

sutures^{****}then the flap was coronally repositioned by sling suturing technique using 5-0 polypropylene^{****}sutures.

**** Assut Sutures, Absorbable (PGA) 5-0 USP, braided violet coated 3/8 rev.cutt.17mm, AM trading.

**** Assut Sutures, non Absorbable (Polypropylene) 5-0 USP, braided violet coated 3/8 rev.cutt.17mm, AM trading, Switzezland

V-Postoperative care:

- All patients received antibiotics for 1 week (Augmentin 1 gm every 12 hours^{\$\$\$\$}, metronidazole^{*****} 500gm every 12 hours) and analgesics (Brufen^{*****} 400 every 8 hours) were prescribed for the patients.
- Patients were instructed to avoid brushing at the surgical site. They were instructed to rinse twice daily with chlorohexidine^{*****} mouthwash the day after surgery.
- Sutures were removed after 2 week.
- Patients were instructed not to brush for another 2 weeks after suture removal and to continue using chlorohexidine mouthwash.
- Patients were instructed to use modified bass technique for tooth brushing after one month from surgery.

^{\$\$\$\$} Augmentin 1gm,Medical union pharmaceuticals(MUP) Egypt under license from ,Glaxosmithkline

^{*****} Flagyl 500 mg, sanafi Aventis Egypt under license of sanafi Aventis French.

^{*****} Brufen 400mg, Al kahira pharm. and chem..Ind.Co. under license from abbott laboratories

^{*****} Hexitol(Chlorohexidine HCL 125mg/100ml)the Arab drug company(ADCO)A.R.E

VI-Postoperative evaluation and assessment:

The patients were recalled every month for examination of the surgical area and for plaque removal when necessary

- Clinical and esthetic parameters were evaluated and scored by a separate blinded operator at 3, 6 and 9 months postoperative.

Esthetic outcome evaluation was done using Root coverage esthetic score (RES) system (Cairo et al. 2009)
the RES include the following parameters

- Level of the gingival margin (**GM**): Zero points = failure of root coverage (gingival margin apical or equal to the baseline recession); 3 points = partial root coverage; 6 points = complete root coverage (**CRC**).
- Marginal tissue contour (**MTC**): Zero points = irregular gingival margin (does not follow the CEJ); 1 point = proper marginal contour/ scalloped gingival margin (follows the CEJ).
- Soft tissue texture: Zero points = scar formation and/or keloid like appearance; 1 point = absence of scar or keloid formation.

Patients: Materials and Methods

- Mucogingival junctional alignment (**MGJ**): Zero points = MGJ not aligned with the MGJ of adjacent teeth; 1 point = MGJ aligned with the MGJ of adjacent teeth.
- Gingival color (**GC**): Zero points = color of tissue varies from gingival color at adjacent teeth; 1 point = color of the tissue is similar to the gingival color of the adjacent teeth

These parameter were measured 3, 6 and 9 post-surgical

Volumetric assessment after 9 months :

Impressions were done using addition silicon impression^{\$\$\$\$\$} material at baseline and 9 months.

These impressions were poured using extra hard stone ***** material. All the stone cast models were digitized using optical scanner. The digital surface models were imported as STL files into the software for volumetric analysis (plastycad, 3diemme, Como, Italy). On each cast 4 fixed points were determined and remained untouched during the observation time. These 4 fixed points defining a

\$\$\$\$\$ Elite HD+ Putty Soft addition silicon Manufacturer Part No: ZHC203000. Zhermack SpA, Italy

*****Rock extra hard stone, Manufacturer Part No: C410339, Zhermack SpA, Italy

Patients: Materials and Methods

base plane for one series of measurements. The relevant area for the measurements of volume changes was defined by the mesial and distal surfaces of adjacent teeth.

[figure not shown]
[figure not shown]

Fig (2): Four fixed points defining a base plane for one series of measurements

The digital images obtained were transferred into digital imaging software, which was used to superimpose and match the images obtained in one coordinate system. For superimposition of different images, the buccal surfaces of the adjacent teeth were used as a reference. The scanned cast images were superimposed and subtracted and the soft tissue volume was determined for any volume changes

Patients: Materials and Methods

To evaluate the differences in form between the preoperative and postoperative casts, the variation between images was calculated by subtracting the corresponding phase images, leaving a phase difference image.

Fig(3): Diagram showing the superimposition for the volumetric assessment of the soft tissue thickness

- All data were collected and statistical analysis was done.

VI-Statistical analysis:

Categorical data were presented as frequencies and percentages and were analyzed using chi square test. Numerical data were tested for normality using Shapiro-Wilk test and were presented as mean and standard deviation values. Parametric data were analyzed using one-way ANOVA followed by Tukey's post hoc test for intergroup comparisons and one-way repeated measures ANOVA followed by Bonferroni post hoc test for intragroup comparisons. Non-parametric data were analyzed using Kruskal-wallis test followed by pairwise comparisons utilizing Mann Whitney U test with Bonferroni correction for intergroup comparisons and Friedman's test of repeated measures followed by multiple pairwise comparisons utilizing Wilcoxon signed-rank test with Bonferroni correction for intragroup comparisons. The significance level was set at $p \leq 0.05$ within all tests. Statistical analysis was performed with IBM SPSS Statistics Version 26 for Windows

††††† IBM Corporation, NY, USA.

‡‡‡‡‡ Statistical Package for Social Science, Inc., an IBM Company.

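### Does measuring volume change over a region set by each patient's neighbouring teeth, with no stated division by area, make the outcome partly a measure of tooth size?

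*Protocol*

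**What the plan says.** Under the heading on volumetric assessment after 9 months, the protocol describes silicone impressions at baseline and 9 months, stone casts, optical scanning and import into volumetric software. Fixed points on each cast define a base plane. The region of interest is then given: "The relevant area for the measurements of volume changes was defined by the mesial and distal surfaces of adjacent teeth". The scans are aligned on the buccal surfaces of the adjacent teeth, and the result is described thus: "The scanned cast images were superimposed and subtracted and the soft tissue volume was determined for any volume changes". No unit, formula or apico-coronal limit follows. The caption of Fig (3) names the target differently: "Diagram showing the superimposition for the volumetric assessment of the soft tissue thickness".

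The inclusion criteria admit Miller "class I or II in anterior and premolar teeth (maxillary or mandibular"). Allocation is by computer-generated randomization, with no stratification by tooth type stated, and "each group included 10 patients". The between-group tests named under statistical analysis are unadjusted.

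**The concern.** Read together, these statements suggest a scaling problem. The region is as wide as the patient's own dentition makes it, the eligible teeth differ in width, and the text ends at a volume. If the same thickness of tissue is gained everywhere, a region 1.3 to 1.6 times as wide (assumed) gives 30% to 60% more volume. Tooth size would then add variance to a small comparison, and a chance imbalance in tooth type could be taken for a treatment difference. The caption's reference to thickness, which is volume divided by area, makes it look as if a step was left out.

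**Working it through.** **Inputs.** From the protocol: 10 patients per group, a patient-specific region, casts at two times, anterior and premolar teeth of both jaws. Not given: region areas, the SD of volume change, the unit, the formula. The only sample-size result, about 4 per group at alpha 0.05 and 80% power, comes without effect size, SD or named outcome. It cannot be reproduced and is not tied to volume. Every CV below is therefore an assumption.

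**1. Gain spread uniformly over the region.** Volume change V = t × A, with mean thickness change t independent of region area A:

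CV_V² = (1 + CV_t²)(1 + CV_A²) − 1

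| CV_t | CV_A | CV_V² | CV_t² | Ratio | 10 / ratio |
|---|---|---|---|---|---|
| 0.40 | 0.15 | 1.16 × 1.0225 − 1 = 0.186 | 0.160 | 1.16 | 8.6 |
| 0.40 | 0.20 | 1.16 × 1.04 − 1 = 0.206 | 0.160 | 1.29 | 7.8 |
| 0.40 | 0.25 | 1.16 × 1.0625 − 1 = 0.2325 | 0.160 | 1.45 | 6.9 |
| 0.80 | 0.20 | 1.64 × 1.04 − 1 = 0.706 | 0.640 | 1.10 | 9.1 |

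The last column is the effective number of patients per arm. The arithmetic behind the concern is right, given this model.

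**2. Gain confined to the treated site.** Let the gain have thickness t_F over a footprint F, with no change in the rest of the region. Then

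V = t_F × F + 0 × (A − F) = t_F × F.

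Apart from scanning and alignment error, A drops out and raw volume carries no region-size noise. The divided measure is V/A = t_F × F/A, which does depend on A. For equal gain in a region 1.3 or 1.6 times as wide, raw volume is unchanged, while the divided value falls to 1/1.3 = 0.77 or 1/1.6 = 0.625 of the other. With a volume CV of 0.40 and a CV of 1/A of 0.20 (which a log-normal area with CV 20% gives), the relative variance of V/A is 1.16 × 1.04 − 1 = 0.206 against 0.160. The increase is again 29%, now caused by dividing.

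**3. Between the two.** Suppose V is proportional to A^b, with b = 1 for uniform and b = 0 for local gain, and let σ² be the variance of log A. On the log scale raw volume picks up b²σ² and the divided measure (1 − b)²σ². These are equal at b = 1/2. Division helps above that value and harms below it.

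**4. Which case does the protocol describe?** It treats a localized recession at one involved tooth. In the surgical protocol the horizontal incision reaches only the facial aspect of the adjacent papillae. In Group I the membrane comes from one 10 ml blood draw that is not scaled to tooth size. The region may be read as taking in the neighbouring teeth, which are not grafted. This leans towards local gain but does not fix b.

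**5. Error rates if gain were uniform.** In simulated two-sample t-tests (40,000 runs, 10 per arm), the divided measure was given 80% power, at a standardised difference of 1.32. With thickness CV 0.5, raw volume has power 77%, 69% and 58% at area CV 0.1, 0.2 and 0.3. Over thickness CVs of 0.3 to 0.8 the range is 43% to 78%. Type I error is 4.6% to 5.1% throughout. The 95% range of chance imbalance in mean area, ±1.96 × CV_A × √(2/10), is ±9%, ±18% and ±26% for those area CVs. It is already part of the between-patient variance that sets the test's standard error.

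**The case for a change.** The strongest reply is that the protocol describes the measurement chain in detail and stops at a volume, so the missing division is a feature of the stated method and not mere silence. The flap also follows the tooth, so a wider tooth probably receives a somewhat larger footprint of new tissue and b is above zero. Dividing would cost one area reading per patient from existing files.

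Part of this stands. Some dependence on tooth width is plausible, the text does end at a volume, and the derivation could be stated more fully. But a b above zero is not enough: division gains precision only if b exceeds 1/2, and nothing in the protocol shows that. The divisor would also be an area whose apico-coronal limit is not stated, so it would bring variation of its own. As to the missing step, the protocol gives neither unit nor formula, its caption names thickness, the figure itself is not in the text available, and the statistical analysis plan, where such a derivation is commonly written down, is not at hand. That an undivided volume is the analysed variable is an inference.

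**Conclusion.** The concern does not hold. The variance increase of 16% to 45% (thickness CV 40%, area CV 15% to 25%) depends on tissue gain being uniform over the whole region, which the protocol does not say and which fits poorly with a localized defect at one tooth. Under local gain the proposed division would itself add variance, 29% in the matching example. Raw volume and mean thickness are thus a trade-off that the document cannot settle. No stated figure is wrong, and no passage contradicts another beyond a caption that uses a looser word.

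Nor is there systematic bias. The measure is a change within the patient, so no tissue change gives no volume change whatever the tooth size. Allocation is randomized, and type I error stays near 5% even in the model that favours the concern. At most some power could be lost on one of several outcomes, to which the sample size is not tied. Stating the unit and the derivation would be a courtesy to the reader, not the correction of a fault.

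### A normality pre-test on 10 patients per arm chooses between means and ranks for each numerical outcome; name the test per outcome in advance and use the baseline value already collected

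*Protocol*

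**What the plan says.** Protocol, VI-Statistical analysis, sets out three steps.

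- Check: "Numerical data were tested for normality using Shapiro-Wilk test and were presented as mean and standard deviation values".
- Means branch: "Parametric data were analyzed using one-way ANOVA followed by Tukey's post hoc test for intergroup comparisons", with repeated-measures ANOVA for comparisons within a group.
- Rank branch: "Non-parametric data were analyzed using Kruskal-wallis test", with Mann-Whitney follow-up between groups, and Friedman and Wilcoxon tests within a group.

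No outcome is assigned to a branch, and nothing except the Shapiro-Wilk result is offered to separate the two kinds of data. The section does not say whether normality is judged per arm, pooled, per visit, on change or on residuals.

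Under Calculation of Power analysis, "each group included 10 patients". Under Clinical parameters Assessments, six parameters are measured at baseline and at 3, 6 and 9 months. RES is scored at 3, 6 and 9 months, and volume is compared between baseline and 9 months.

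**The concern.** The analysis of each numerical outcome depends on a preliminary test of the trial's own data. Three things follow.

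- **The hypothesis is not fixed in advance.** ANOVA compares means and Kruskal-Wallis compares ranks. Which one an outcome receives is known only once the data are in. It can differ between outcomes and, if the check is made per visit, between visits of one outcome.
- **The pre-test cannot do the job at this size.** With 10 values it often misses real skewness, and it can fail normal data because the scale is coarse.
- **Some answers need no test.** Plaque index and gingival index are ordinal scores. RES adds a gingival-margin item worth 0, 3 or 6 to four items worth 0 or 1, so it runs from 0 to 10 in whole points. The section also summarises all numerical data by mean and SD, so an outcome tested on ranks would still be described by its mean.

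At stake is a pre-specified, consistent comparison. Both branches also leave the baseline measurement out of the between-arm comparison.

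**Working it through.** **Inputs from the protocol.** 10 patients per arm; significance at 0.05; four assessments of the clinical parameters; two branches as above. With two groups, one-way ANOVA is the equal-variance t-test (F = t², 1 and 18 degrees of freedom).

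**Assumptions, because the protocol gives no figure.** Outcome distributions, SD, reading unit, correlation with baseline, and the working rule that ranks are used if either arm fails Shapiro-Wilk at 0.05. Results are from 4,000 to 6,000 simulated trials per setting, and 2,000 to 4,000 for the four-visit runs.

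**The plan's own figure.** The section on power states that "the estimated minimum required sample size was approximately 4 cases in each group" at 80% power, without an effect size or SD. Inverting n = 2(1.960 + 0.842)²/d² at n = 4 gives d = 2.802 × √(2/4) = 1.98. The figure can be neither confirmed nor called wrong, and nothing below depends on it: the pre-test would be run on the 10 per arm enrolled.

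**1. What the pre-test detects in 10 values.**
- Normal data: one arm fails in 5% of runs. Either arm fails in 1 − 0.95² = 0.0975; simulated 0.099.
- Lognormal (log-SD 0.5): one arm fails in 25%, so the skewness is missed in 75%.
- Exponential: one arm fails in 45%.
- Gamma, shape 1.5: both arms pass as normal in 47-48% of trials.

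**2. Effect of coarse recording on normal data, one arm failing.**
- Whole-unit reading: 45-48% at SD 1, 19% at SD 1.5, 12% at SD 2.
- Half-unit reading at SD 1: 11-12%.

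**3. Consistency across four visits, only if the check is made per arm and visit.** For normal data and independent visits, the chance that visits split between tests is 1 − 0.9025⁴ − 0.0975⁴ = 1 − 0.6634 − 0.0001 = 0.34. Simulated: 0.29-0.33 for correlations from 0 to 0.8. For whole-unit reading at SD 1: 0.62-0.74.

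**4. Error and power of the rule followed strictly.**
- Type I error: 0.043-0.061 over the distributions tried, against 0.042-0.054 for always ANOVA and 0.043-0.063 for always ranks. Taking the smaller of the two p-values gives 0.051-0.064.
- Power, normal data, 1 SD shift: rule 0.565, ANOVA 0.566, ranks 0.548.
- Power, gamma data, 1 SD shift: rule 0.684, ANOVA 0.59-0.60, ranks about 0.69. The two tests disagree at 0.05 in 13-14% of these trials.

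**5. What baseline adjustment adds.** ANCOVA multiplies the residual variance by (1 − ρ²), where ρ is the correlation of follow-up with baseline, and uses one degree of freedom (18 becomes 17). A 1 SD shift then acts like:
- ρ = 0.3: 1/√0.91 = 1.05 SD
- ρ = 0.5: 1/√0.75 = 1.15 SD
- ρ = 0.7: 1/√0.51 = 1.40 SD

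Simulated power, ANCOVA against the rule:
- Normal data: 0.59 v 0.58 at ρ = 0.3; 0.64-0.82 v 0.56-0.58 at ρ = 0.5-0.7.
- Gamma data: 0.68-0.81 v 0.68-0.69 at ρ = 0.5-0.7. At ρ = 0.3, a run of 4,000 trials gave about 0.62 v 0.69.

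**The case against.** The strongest reply is that the rule does little harm. Its type I error is close to nominal, and its power is close to that of the better unadjusted test in both settings. Where both arms pass despite gamma skewness, ANOVA and ranks have about the same power (0.672 v 0.675). All of this stands. A reader might infer from 0.60 for ANOVA against 0.69 for ranks that the pre-test wastes power; the rule's own 0.684 shows that it does not. A reader might also infer inflated false positives, and the figures do not support that either.

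Second, the section puts between-group and within-group tests under one label, and repeated-measures ANOVA or Friedman needs a single choice across visits within an arm. One classification per variable is thus a natural reading. Switching between visits is something the text leaves open, not something it prescribes, and the split figures are conditional on a per-visit check.

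Third, the rounding figures depend on an SD and reading unit that the protocol does not give; the range from 11% to 48% shows how much.

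Fourth, a mean-based default would lower power in skewed data, from 0.684 to 0.594. That applies to an unadjusted test. With adjustment the loss disappears at correlations of 0.5 or more, but not at low correlation.

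Finally, the unit on which normality is tested is ordinary SAP detail, and its absence is not the point. The selection rule itself is stated in the protocol.

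**Conclusion.** The point holds as one of pre-specification and efficiency. The protocol lets a Shapiro-Wilk test on 10 patients per arm decide between means and ranks, and that test is close to uninformative here: it misses clear skewness in both arms in about 48% of trials and can react to recording precision alone. The documents do not support a claim that the rule distorts error rates, costs appreciable power against the better unadjusted test, or requires the method to change between visits.

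The change is worth making because it fixes the hypothesis for each outcome before the data are seen. For the probe measurements it also adds precision that neither branch uses: on normal data, power for a 1 SD shift rises from 0.56-0.58 to 0.64-0.82 if the correlation with baseline is 0.5-0.7. That correlation, the distributions and the SD are assumptions. The protocol implies rather than spells out that Shapiro-Wilk is the switch, but it offers no other criterion.

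**What to change.** Remove the normality test as a rule for choosing the analysis, and replace it with one named comparison per outcome:

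- **Recession depth, keratinized tissue width, PD, CAL:** ANCOVA of the follow-up value on arm and baseline value, the same method at 3, 6 and 9 months, with a rank test as a stated sensitivity analysis.
- **Volume change at 9 months:** one between-arm test, named in advance.
- **Plaque index, gingival index, RES:** rank tests, summarised by median and quartiles instead of mean and SD.

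Shapiro-Wilk results or residual plots may still be reported as description.

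Cost: a few lines of text, no new data, and one degree of freedom for the covariate. If the correlation with baseline is low there is little or no power gain (0.59 v 0.58 at 0.3, normal data), and with skewed data as well ANCOVA can fall below the present rule (about 0.62 v 0.69). The rank sensitivity analysis would make that visible but would not restore the power of the main test.

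### Between-group tests of recession depth, keratinized tissue width, CAL and PD do not adjust for the measured baseline, which leaves a trial of 10 per arm exposed to chance imbalance

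*Protocol*

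**What the plan says.** Under III- Clinical parameters Assessments, the protocol lists plaque index, gingival index, probing depth (PD), clinical attachment level (CAL), recession depth and keratinized tissue width, all recorded "preoperative (baseline), 3, 6 and 9 months after the surgical procedure". Under Calculation of Power analysis, "each group included 10 patients"; randomisation is computer generated, and no stratification is described.

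Section VI-Statistical analysis gives the tests:

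- **Between arms, parametric:** "Parametric data were analyzed using one-way ANOVA followed by Tukey's post hoc test for intergroup comparisons".
- **Between arms, non-parametric:** "Kruskal-wallis test followed by pairwise comparisons utilizing Mann Whitney U test with Bonferroni correction for intergroup comparisons".
- **Within an arm, parametric:** "one-way repeated measures ANOVA followed by Bonferroni post hoc test for intragroup comparisons", with Friedman and Wilcoxon tests as the non-parametric counterpart.

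No ANCOVA or other baseline adjustment appears. The text does not say whether the between-arm tests use the follow-up value or the change from baseline.

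**The concern.** For the four parameters, the named between-arm tests have no place for a covariate. The only stated tests that bring in baseline are the within-arm ones, and those cannot show whether L-PRF and connective tissue graft differ. The natural reading is an unadjusted comparison of follow-up values. If changes are compared instead, baseline is subtracted but still not adjusted for as a covariate.

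Two things are at stake with 20 patients. First, a chance difference in starting recession or tissue width carries over into the follow-up difference in proportion to the correlation between the two measurements. Second, variation that baseline could explain stays in the error term and widens the interval for the treatment difference.

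The point does not reach the other outcomes:

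- **Volume** is already a change from baseline: "The scanned cast images were superimposed and subtracted".
- **The root coverage esthetic score** has no baseline value.
- **Plaque and gingival index** are both brought to 1 or below before surgery.

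With only two arms, the Tukey and Bonferroni-pairwise steps between groups are redundant and change no p-value.

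**Working it through.** **Inputs.** From the protocol: 10 patients per arm, significance level 0.05, baseline measured. Assumed, because the protocol does not give them: two-sided tests, no dropout, equal SDs at baseline and follow-up, normal data, and a baseline-to-follow-up correlation r from 0 to 0.7.

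**The plan's own figure.** The protocol states a minimum of about 4 per group for 80% power but gives no difference, SD or endpoint, so the figure cannot be reproduced. Solved backwards with a two-sided t test, it implies a difference of about 2.38 SD. With 10 per arm, 80% power corresponds to 1.325 SD. The results below do not depend on the planned effect.

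**Step 1: size of a chance imbalance.** The standard error of the baseline difference is √(1/10 + 1/10) = 0.447 SD. Then P(|difference| > 0.5 SD) = 2 × [1 − Φ(0.5/0.447)] = 0.264.

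**Step 2: carry-over.** With follow-up values, a baseline difference of 0.5 SD shifts the expected follow-up difference by r × 0.5 SD: 0.15, 0.25 and 0.35 SD at r = 0.3, 0.5 and 0.7. With change scores the shift is (1 − r) × 0.5 SD in the opposite direction: 0.35, 0.25 and 0.15 SD.

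**Step 3: false-positive rate when the imbalance exceeds 0.5 SD** (simulation).

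| r | follow-up value | change score | ANCOVA |
|---|---|---|---|
| 0.3 | about 7% | about 11% | about 5% |
| 0.5 | about 10% | about 10% | about 5% |
| 0.7 | about 13% | about 8% | about 5% |

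Over all trials, each method has a rate of about 5%.

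**Step 4: precision.** With N = 20, the ANCOVA variance relative to the unadjusted follow-up comparison is (1 − r²)(N − 3)/(N − 4) = (1 − r²) × 17/16. At r = 0.5 this is 0.75 × 1.0625 = 0.797. For the change score the ratio is 2(1 − r). The ratio of interval widths is the square root of the ANCOVA variance ratio times 2.110/2.101, the t quantiles on 17 and 18 degrees of freedom.

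| r | ANCOVA variance ratio | CI width, ANCOVA vs unadjusted | change-score variance ratio |
|---|---|---|---|
| 0 | 1.06 | 103% | 2.0 |
| 0.3 | 0.97 | 99% | 1.4 |
| 0.5 | 0.80 | 90% | 1.0 |
| 0.7 | 0.54 | 74% | 0.6 |

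Break-even with follow-up values is at 1 − r² = 16/17, so r = 0.24 on variance; on interval width it is 0.26. Against change scores, the ratio is (1 + r) × 17/32, so ANCOVA is more precise for r below 15/17 = 0.88.

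**Step 5: power for a true difference of 1 SD.**

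| r | follow-up value | change score | ANCOVA |
|---|---|---|---|
| 0 | 56% | 32% | 54% |
| 0.3 | 56% | 43% | 58% |
| 0.5 | 56% | 56% | 66% |
| 0.7 | 56% | 78% | 82% |

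**Step 6: floor at complete coverage.** The esthetic score has a category for full coverage ("6 points = complete root coverage"), so many sites may end at zero recession. Follow-up recession was cut at zero, with an assumed 50% of the better arm fully covered. The unadjusted rank test then has 52–53% power. ANCOVA on ranks has about 50%, 54%, 59% and 71% at an underlying r of 0, 0.3, 0.5 and 0.7, and its false-positive rate stays close to 5%. With 80% assumed fully covered, the gain is nil at r = 0.3, about 4 to 5 points at 0.5 and about 12 points at 0.7.

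**The case against.** The strongest reply is that no error has been shown. With two groups, one-way ANOVA is the t test, a legitimate comparison of randomised arms with a 5% false-positive rate overall. That is right: this is a matter of robustness and precision, not of bias or of an invalid test. The protocol does name its tests, however, so the point concerns a stated method and not a detail left to a statistical analysis plan.

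Second, the conditional rates describe the unlucky 26% of trials. Since the overall rate is 5%, the other 74% must fall below it. At r = 0.5 the rate there is about (5 − 0.264 × 9.5)/0.736 = 3.4%. This stands as a caution on how to read the figures. The investigator will nevertheless see whether the baseline is unbalanced, and the unadjusted test cannot respond to it.

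Third, the correlation is unknown, and the gain may be small. This stands in part. It is small for recession depth if most sites reach complete coverage. It may also be small for PD, whose baseline range is probably narrow because periodontitis is an exclusion and scaling precedes surgery. The possible loss is 1 to 3 points of power, against gains of 10 points at r = 0.5 and 26 at r = 0.7 without a floor.

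Fourth, the team may analyse changes. The false-positive rate under imbalance is then raised as well (Step 3), and power is lower than with ANCOVA at every correlation shown.

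Finally, the protocol is written in the past tense. If outcome data have already been seen, an added covariate is a later analysis and must be labelled as one.

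**Conclusion.** The concern holds as a recommended improvement. For recession depth, keratinized tissue width, CAL and PD, the stated between-arm tests leave a collected baseline unused as a covariate. They remain valid on average. The weakness is that about one trial in four of this size starts with an imbalance above 0.5 SD that the test cannot correct, and that precision is lost at moderate correlation: at r = 0.5 the unadjusted variance is about 25% larger (1/0.797).

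The probability of imbalance needs only the 10 per arm and approximate normality of the baseline mean difference. All other figures rest on the assumed correlation, and the power figures also on normal data or, for the floor check, on an assumed share of complete coverage. Below a correlation of about 0.25, adjustment brings no gain in precision.

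**What to change.** In VI-Statistical analysis, for recession depth, keratinized tissue width, CAL and PD:

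- Compare the arms by ANCOVA, with group as factor and the same parameter's baseline value as covariate, at 9 months and likewise at 3 and 6 months. Report the adjusted difference with its 95% confidence interval.
- Keep Shapiro-Wilk as the stated trigger for the non-parametric route, and use ANCOVA on ranks there. Ranks give no interval in millimetres, so the interval applies to the unranked analysis only. Note that ANCOVA assumes parallel slopes, which may fail if one arm reaches complete coverage much more often.
- State that within-arm tests are descriptive and are not evidence of a difference between arms.

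Keep the stated two-group tests for plaque index, gingival index, the esthetic score and volume change. Drop the Tukey and Bonferroni-pairwise wording between groups.

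The cost is a change of wording: the data are already collected, and the named software can run the analysis. One degree of freedom goes to the covariate, with 1 to 3 points of power lost if the true correlation is below about 0.25. If results are already known, report the adjusted analysis beside the stated one and mark it as added later.
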